5.3. Study Population

5.3.1. Patient Disposition

For All Treated Population, the number of patients in each patient disposition will be summarized for each cohort. The patient disposition table will include the number of patients treated at data cutoff, the number of patients with treatment ongoing at data cutoff, and the number of discontinued patients along with the reason for study discontinuation.

5.3.2. Demographic and Other Baseline Characteristics

For the All Treated Population, the following baseline characteristics will be summarized for each cohort.

For all cohorts:

- Age
- Age category (< 65, \geq 65)
- Sex (Male, Female)
- Ethnicity (Hispanic/Latino, Not Hispanic/Latino, Unknown, Not collected)
- Race (Caucasian/White, Black or African American, Asian, American Indian or Alaska Native, Native Hawaiian or Other Pacific Islander, Not collected, Other)
- ECOG PS (0, 1)
- Baseline height
- Baseline weight

- Prior surgery (Yes, No)
- Prior radiotherapy (Yes, No)
- Prior systemic anticancer therapy (Yes, No)
- Number of prior lines of systemic therapy

For Cohort A:

- Primary cancer type
- Histology
- Any metastases (Yes, No)
- *FGFR* Receptor (*FGFR1*, *FGFR2*, *FGFR3*, *FGFR4*)
- *FGFR* Rearrangements including fusion
 - Rearrangement or fusion
 - Fusion partner

For Cohort B:

- Primary cancer type (Gastric, GEJ, Both)
- Location of Primary Tumor (Z-line, Cardia, Fundus, Body, Antrum, Pylorus, etc.)
- Histology (Papillary adenocarcinoma, Tubular adenocarcinoma, Mucinous adenocarcinoma, Signet-ring carcinoma, etc.)
- Histology subtype (Intestinal, Diffused, Mixed)
- Tumor grade (Well-, Moderately-, Poorly differentiated)
- Any metastases (Yes, No)
- *FGFR2* amplification as detected locally by FISH, PCR, NGS or IHC
- *FGFR2* copy number and/or *FGFR2/CEN10* ratio

For Cohort C:

- MLN Characteristics (MLN only, Lymphoma presentation, Leukemia presentation)
- Eosinophilia (Yes, No)
- Thrombocytosis (Yes, No)
- Extramedullary disease (Yes, No)
- Blast Phase (Yes, No)
- Active CNS involvement related to primary disease (Yes, No)
- Palpable Splenomegaly (Yes, No)
- Palpable Hepatomegaly (Yes, No)
- Hematopoietic Stem Cell Transplantation (Yes, No)

- *FGFR1* rearrangements (including fusions)
 - Rearrangement or fusion
 - Fusion partner

5.3.3. Medical History

Medical history will be coded according to the Medical Dictionary for Regulatory Activities (MedDRA; the most up-to-date version at the time of analysis).

For the All Treated Population, medical history will be summarized by System Organ Class (SOC) and preferred term for each cohort.

5.3.4. Prior Anticancer Therapy

For the All Treated Population, the following analyses will be performed for each cohort:

- Prior anticancer surgery will be summarized. The number and percentage of patients with at least one anticancer surgery for primary disease will be presented. The type of surgery and the time from prior surgery to the first dosing date will be summarized.
- Prior radiation therapy for primary disease will be summarized. The number and percentage of patients with at least one prior radiation therapy for primary disease will be presented. The intent of the radiotherapy, site location of the radiotherapy, duration of the radiotherapy, and time from the end date of the radiation therapy to the first dosing date will be summarized.
- Prior anticancer therapy for primary disease will be summarized. The number and percentage of patients with at least one prior anticancer therapy for primary disease will be presented. The treatment type and therapy type will be summarized. The analysis described below will be repeated for each treatment type (Adjuvant, Neoadjuvant, Advanced/Metastatic disease, Maintenance therapy, or Other) in separate tables. The best response to therapy (CR, PR, SD, PD, or NE), the reason for the therapy discontinuation, duration of the anticancer therapy, and time from the end date of the anticancer therapy to the first dosing date will be summarized.

5.4. Concomitant Medication and Therapy

Medications taken on or after the first dose of study drug through 30 days after the last dose of study drug are considered concomitant medications and therapies. In addition, medications that started prior to the first dose of the study drug and continued into the treatment period are considered concomitant medications and therapies.

For the All Treated Population, the number and percentage of patients who received concomitant medications for management of hyperphosphatemia will be summarized by medication class and generic term for each cohort. The total duration of medications (excluding overlaps of duration) for management of hyperphosphatemia will also be summarized.

5.5. Efficacy Analyses

All efficacy analyses will be performed for each cohort using All Treated Population, unless otherwise specified.

5.5.1. Cohorts A and B

The description of each efficacy endpoint for Cohorts A and B is provided in [Table 8](#).

Table 8: Efficacy Endpoint Definitions for Cohorts A and B

Endpoint	Definition
ORR	The proportion of patients experiencing a best overall response of PR or CR (per RECIST 1.1), based on IRC and Investigator assessment
DCR	The proportion of patients experiencing a best overall response of SD, PR, or CR (per RECIST 1.1), based on IRC and Investigator assessment
DOR	The time from the first documentation of response (CR or PR per RECIST 1.1 based on IRC and Investigator assessment) to the first documentation of objective tumor progression or death due to any cause, whichever occurs first
PFS	The time from first dose of study therapy to the date of death (any cause) or disease progression (based on IRC and Investigator assessment), whichever occurs first
OS	The time from the date of first dose to the death date

5.5.1.1. Primary Efficacy Analysis

ORR based on IRC will be calculated, and the 2-sided 95% CI will be derived by Clopper–Pearson method.

ORR will be calculated based on the best overall response recorded from the start of treatment until progression disease or start of subsequent new anticancer treatment. The overall response can be derived based on target lesion response, non-target lesion response and the emergence of a new lesion for patients with measurable disease at baseline.

The best objective response of CR and PR will be confirmed with at least 4 weeks intervals of two consecutive time points. A minimum of a 6-week interval between initial of treatment (first dose date) and tumor measurement is required for SD. If applicable, responses recorded after disease progression or initiation of new anticancer treatment will be excluded. The confirmation rule of the best overall response is shown in [Table 9](#).

Table 9: Confirmation Rules for Overall Response of PR and CR

Earlier Response (to be confirmed)	Later Response (confirmation)	Confirmed Response
CR	CR ^a	CR
CR	Not CR or missing ^b	SD
PR	CR or PR ^a	PR
PR	SD or PD or missing ^b	SD
PR	SD and then PR (only one SD in between) ^a	PR

Earlier Response (to be confirmed)	Later Response (confirmation)	Confirmed Response
SD	n/a – no confirmation needed ^b	SD
PD	n/a – no confirmation needed	PD

^a: A minimum of 4-week interval between two tumor measurements is required to confirm PR or CR.

^b: A minimum of 6-week interval between initial of treatment (first dose date) and tumor measurement is required for SD

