- If it is not possible to have assessments performed at a local facility, the patient may be evaluated for safety via a phone call or video call, assuring the collection and follow-up of adverse events is documented in the patient's source file. All C1 assessments need to be performed. For C2 and beyond, a patient will not receive additional treatment without having laboratory and ECG assessments performed at least once during each cycle (eg, on C1D1).
- Response assessments will need to be performed, as often as the circumstances allow, according to the protocol. If the patient is not able to visit the study site, alternatively, a local qualified imaging facility can be used.

- The results, including the images obtained from all radiographic procedures, should be sent to the Investigator. The imaging facility used, the timepoints, and the Investigator's review of the images should be documented in the patient's source files and the eCRF.
- If a patient is diagnosed with COVID-19 or develops symptoms suggesting COVID-19, patients will be managed according to local guidelines. Symptomatic COVID-19 cases will be reported as AEs or SAEs; it is at the Investigator's discretion to report asymptomatic COVID-19 cases. In the case of patients diagnosed with COVID-19 (symptomatic or asymptomatic), patients can only continue treatment with futibatinib if the Investigator considers that there is an individual positive risk/benefit balance, and once the patient has fully recovered from the COVID-19 infection. The Sponsor should be made aware of the Investigator's decision.

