8.1.5. Objective Response Assessment

Assessments will be based on the definitions provided in [Table 12](#) and [Table 13](#). Since this is a non-randomized study, all responses (CR/PR) must be confirmed.

Table 12: Time Point Response for Patients with Target (\pm Non-target) Disease

Target Lesions	Non-Target Lesions	New Lesions	Objective Response
CR	CR	No	CR
CR	Non-CR/Non-PD or Not all evaluated	No	PR
PR	Non-PD or Not all evaluated	No	PR
SD	Non-PD or Not all evaluated	No	SD
Not all evaluated	Non-PD	No	NE
PD	Any	Yes or No	PD
Any	PD	Yes or No	PD
Any	Any	Yes	PD

Abbreviations: CR=complete response; NE=not evaluable; PD=progressive disease; PR=partial response; SD=stable disease

Table 13: Time Point Response for Patients with Only Non-target Disease

Non-Target Lesions	New Lesions	Objective Response
CR	No	CR
Non-CR/Non-PD	No	SD
Not all evaluated	No	NE
Unequivocal PD	Yes or No	PD
Any	Yes	PD

Abbreviations: CR=complete response; NE=not evaluable; PD=progressive disease; PR=partial response; SD=stable disease

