11.5.3.1. Cohorts A and B

11.5.3.1.1. Primary Efficacy Analysis

Objective response rate is defined as the proportion of patients with objective evidence of CR or PR (per RECIST 1.1). The evaluation of ORR will be based on an independent central review of radiologic images. At the analysis stage, the best objective response will be assigned for each patient as the best response recorded after initiation of study drug and confirmed at least 4 weeks later. If applicable, responses recorded after disease progression or initiation of new anticancer treatment will be excluded. The exact 2-sided CI based on Clopper-Pearson methodology will be derived for ORR.

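### Read literally, SAP Table 9 turns a response into SD when one missed or non-evaluable scan separates two qualifying scans, or when a CR is followed by a PR caused only by incomplete non-target evaluation.

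*SAP*

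**What the plan says.** Protocol section 8.1.5 states that "all responses (CR/PR) must be confirmed". Protocol section 11.5.3.1.1 takes the "best response recorded after initiation of study drug and confirmed at least 4 weeks later". It sets a minimum interval and does not require the two scans to be adjacent.

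SAP section 5.5.1.1 is tighter: "The best objective response of CR and PR will be confirmed with at least 4 weeks intervals of two consecutive time points". Footnote a to Table 9 repeats only the interval: "A minimum of 4-week interval between two tumor measurements is required to confirm PR or CR". The rows of Table 9 that matter here are:

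- An earlier CR with a later response of "Not CR or missing" is SD.
- An earlier PR with a later response of "SD or PD or missing" is SD.
- An earlier PR with a later CR or PR is PR.
- An earlier PR followed by "SD and then PR (only one SD in between" is PR.

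No row covers an NE assessment, or a missed scan followed by a further response. SAP section 5.5.1.2 applies the same rule to Investigator-assessed ORR.

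**The concern.** A patient with two scans at least 4 weeks apart, both meeting PR or better, can be counted as a non-responder because the scan between them was missed or unreadable. The same patient with an SD reading in between would be a responder. Protocol section 6.3 accepts that gaps may occur: "Response assessments will need to be performed, as often as the circumstances allow, according to the protocol".

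A related case needs no missed visit. Protocol Table 12 makes a time point PR when target lesions are in CR but non-target lesions were not fully evaluated. A CR followed by such a scan is SD under Table 9, although the tumour may not have changed.

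At stake is the numerator of the primary endpoint in Cohorts A and B. A patient reclassified this way stays in the All Treated denominator, still counts in DCR as SD if the 6-week minimum is met, and drops out of the DOR analysis, which the protocol names as key secondary.

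**Working it through.** **1. Applying Table 9 literally to sequences of scans 8 weeks apart, with nothing after the last scan shown**

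| Sequence | Table 9 result |
|---|---|
| PR, SD, PR | PR |
| PR, missing, PR | SD |
| CR, missing, CR | SD |
| CR, PR | SD |
| PR, CR | PR |
| PR, missing, PR, PR | PR (rescued by the later pair) |
| CR, PR, PR | PR (rescued by the later pair) |

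If a missed scan is skipped and not treated as a time point, PR-missing-PR becomes PR and CR-missing-CR becomes CR. CR-PR stays SD on either reading.

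**2. Comparison with the SAP's own tolerance for gaps**

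Footnote c to SAP Tables 10 and 12 (PFS and DOR) treats two or more assessments as missed when a gap exceeds (28 × 2 + 7) × 2 = 126 days. One missed scan gives a nominal gap of 2 × 56 = 112 days, or 112 + 7 + 7 = 126 days with both visit windows used in full. PFS and DOR therefore accept one missed scan. Read literally, Table 9 does not.

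**3. Reproducing the plan's figures**

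Inputs from protocol section 11.1: Cohort A has N = 100, null ORR 10%, target 25%, success at 17 or more responders. Cohort B has N = 35, null 10%, target 35%, success at 8 or more. Power is the exact binomial tail P(X ≥ r | N, p).

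- Cohort A: P(X ≥ 17 | 100, 0.25) = 97.9% (stated as over 90%). At p = 0.10 the tail is 2.06%.
- Cohort B: P(X ≥ 8 | 35, 0.35) = 95.8% (stated as about 96%). At p = 0.10 the tail is 2.00%.
- Clopper-Pearson 95% limits: 17/100 gives 10.2% to 25.8%, and 8/35 gives 10.4% to 40.1%. Both match the protocol.

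**4. Effect of losing a fraction f of responders**

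The documents do not give f, so 0 to 10% is an assumed range. Replace p with p × (1 − f):

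| f | Cohort A: p, power | Cohort B: p, power |
|---|---|---|
| 0 | 25.0%, 97.9% | 35.0%, 95.8% |
| 2% | 24.5%, 97.3% | 34.3%, 95.0% |
| 5% | 23.75%, 96.0% | 33.25%, 93.5% |
| 10% | 22.5%, 92.9% | 31.5%, 90.3% |

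At the target rates, f = 10% means 0.10 × 25 = 2.5 expected responders in Cohort A and 0.10 × 12.25 = 1.2 in Cohort B. With the Stage 1 rule of at least 4 of 35 included, Cohort A power goes from 96.9% (f = 0) to 91.1% (f = 10%). Cohort A's type I error falls from 2.06% to 0.78% at f = 10% (single-stage calculation).

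**5. At the boundary**

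One lost responder moves 17/100 (lower limit 10.2%) to 16/100 (9.4%), and 8/35 (10.4%) to 7/35 (8.4%). Neither lower count excludes 10%.

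**The case against.** Four arguments count against the point.

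*The missed-scan reading is not the only one.* In Table 9, missing may mean that no later scan exists. The footnotes to the PFS and DOR tables use consecutive for scans actually performed, whatever the gap. On that usage PR-missing-PR is already a confirmed PR. This is fair, and it is why the point rests on the literal text. But the SAP does not say which meaning applies, and the exception written for one SD suggests that other interruptions are not excused. A primary-endpoint rule should not leave this to the programmer.

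*The different treatment of SD and missing can be defended.* An observed SD shows that the disease had not progressed at that visit, and a missed scan shows nothing. Yet the later PR, read against the nadir with no PD recorded, supplies much of that evidence. The SAP accepts the same gap for PFS and DOR.

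*A reader might infer that every CR-then-PR patient is wrongly lost.* The documents do not support that. The SD row is an explicit, conservative choice under an ORR defined per RECIST 1.1, and true reappearance of disease after a CR is arguably not a confirmed PR. PR-CR and CR-PR-PR already count as PR. The sub-case that the documents clearly support is the PR produced only by incomplete non-target evaluation.

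*A reader might also infer that the design is underpowered.* It is not. At the design ORR of 25%, Cohort A keeps more than 90% power even at f = 10%. Larger losses appear only at a true ORR of 20%, which is not the design alternative. Because confirmation is already mandatory, the 25% may itself be a confirmed rate, in which case some of the loss is already allowed for. The boundary effect of one responder is true of any rule.

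**Conclusion.** The point holds in a limited form. On its literal text, Table 9 scores PR-missing/NE-PR and CR-missing/NE-CR as SD when no later pair confirms. That is stricter than protocol section 11.5.3.1.1 and out of line with the SAP's own PFS and DOR rules. It also scores as SD a CR followed by a PR that reflects only incomplete non-target evaluation.

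The result is a downward, conservative bias in the primary ORR of Cohorts A and B. It cannot produce a false claim of efficacy. Its size is unknown and probably small, since a later confirming pair rescues a patient. The power figures rest on the assumed 0 to 10% range, on the protocol's 100 patients in Cohort A (the SAP still describes 60), and on the target rates being what would be observed with no such losses. The matter is worth correcting because it concerns the primary endpoint and costs little, not because the trial's conclusions are in general danger.

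**What to change.** Amend SAP Table 9 and the sentence above it:

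- PR or CR, then one missing or NE assessment, then PR or CR at least 4 weeks after the first and before PD or new anticancer therapy: confirmed at the lower of the two responses.
- Restrict missing, in the SD rows, to no further adequate assessment.
- CR followed by a PR due only to incomplete evaluation of non-target lesions: confirmed PR.
- Leave CR followed by real reappearance of disease to RECIST 1.1.
- State whether consecutive refers to scheduled or evaluable time points, so that the text agrees with the table and with protocol section 11.5.3.1.1.

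The cost is a few table rows and the matching programming for IRC and Investigator response. No new data are needed, and the SAP has to be revised anyway for the Cohort A sample size. The real risk is timing: the change can only add responders, and the trial is open-label with sponsor review of Cohort A. It should therefore be fixed before responses are tabulated, and ORR under Table 9 as it now stands should be reported as a sensitivity analysis.

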5.5.1.2. Secondary Efficacy Analyses

- ORR based on Investigator assessment will be calculated and the 2-sided 95% CI will be derived by the Clopper–Pearson method. The confirmation rule of CR and PR is the same as the primary endpoint.
- DCR based on IRC and Investigator assessment will be calculated and the 2-sided 95% CI will be derived by the Clopper–Pearson method. The confirmation rule of CR and PR is the same as the primary endpoint. A minimum of a 6-week interval is required between the first dosing date and the first SD.
- PFS based on IRC and Investigator assessment will be estimated using the Kaplan–Meier method. Patients who did not progress or die will be censored on the date of their last tumor assessment. Patients who did not have any post-baseline assessments will be censored on the first dosing date. Patients who started any subsequent anti-cancer therapy without a prior reported progression will be censored at the last tumor assessment prior to initiation of the subsequent anti-cancer therapy. The censoring rule for PFS is in [Table 10](#).
- Overall survival will be estimated using the Kaplan–Meier method. In the absence of confirmation of death or for patients who are alive as of the OS cut-off date, survival time will be censored at the last known date that the patient was alive. The censoring rule for OS is in [Table 11](#).
- DOR based on IRC and Investigator assessment will be evaluated only in patients with an objective response of CR or PR. The starting time point is the first documentation of response (CR or PR). DOR will be estimated using the Kaplan–Meier method. Patients who are alive and progression-free as of the data cut-off date will be censored at their last evaluable tumor response assessment. Patients who start subsequent anticancer therapy without a prior reported progression will be censored at the last tumor assessments prior to initiation of the subsequent anticancer therapy. The censoring rule for DOR is described in [Table 12](#).

Table 10: Censoring Rules for Progression-Free Survival (PFS)

No.	Situation	End Date	Outcome
1	Documented PD between scheduled visits	Date of the first assessment that determined PD	PFS event
2	Death during the study with no prior PD	Date of death	PFS event
3	Patients still on treatment without PD as of data cut-off ^a	Date of the last tumor assessment ^b	Censored

No.	Situation	End Date	Outcome
4	Treatment discontinuation for reasons other than PD or death, and no post baseline tumor assessments	Date of the first dose	Censored
5	Treatment discontinuation for reasons other than PD or death with post baseline tumor assessments	Date of the last tumor assessment	Censored
6	New anticancer treatment started	Date of the last tumor assessment before start of new treatment	Censored
7	Death or PD after two or more missed tumor assessments ^c	Date of the last tumor assessment before missed assessments	Censored
8	No baseline or unreadable baseline assessment but readable post baseline assessments	Date of the first dose	Censored

^a This refers to patients who were still receiving study treatment at time of data cutoff.

^b For PFS analysis, the date of last tumor assessment refers to the date of last adequate tumor assessment.

^c Two or more missed tumor assessments is defined as having either one of the following two durations being longer than 126 days (= (28 [days/cycle] x 2 [cycles] + 7 [days]) x 2):

Duration between two consecutive tumor assessments

Duration between the last tumor assessment and death or PD

Table 11: Censoring Rules for Overall Survival (OS)

No.	Situation	End Date
1	Death before cut-off	Date of death
2	Death after data cut-off	Date of data cut-off
3	Patient still alive at data cut-off	Date of data cut-off
5	Patient discontinued treatment due to any reason before data cut-off	Date last known to be alive

Table 12: Censoring Rules for Duration of Response (DOR)

No.	Situation	End Date	Outcome
1	Documented PD between scheduled visits	Date of the first assessment that determined PD	DOR event
2	Death during the study with no prior PD	Date of death	DOR event
3	Patients still on treatment without PD as of data cut-off ^a	Date of the last tumor assessment ^b	Censored
4	Treatment discontinuation for reasons other than PD or death	Date of the last tumor assessment	Censored

No.	Situation	End Date	Outcome
5	New anticancer treatment started	Date of the last tumor assessment before start of new treatment	Censored
6	Death or PD after two or more missed tumor assessments ^c	Date of the last tumor assessment before missed assessments	Censored

^a This refers to patients who were still receiving study treatment at time of data cutoff.

^b For DOR, the date of last tumor assessment refers to the date of last adequate tumor assessment.

^c Two or more missed tumor assessments is defined as having either one of the following two durations being longer than 126 days (= (28 [days/cycle] x 2 [cycles] + 7 [days]) x 2):

Duration between two consecutive tumor assessments

Duration between the last tumor assessment and death or PD

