Prior & concomitant medications, AE assessments		→													
Physical examination	X	X				X		X	X		Within 24 hours prior to dosing.				
Vital signs	X	X				X		X	X		Heart rate, blood pressure, body temperature, and respiration rate.				
Height and weight	X	X				X		X	X		Height at screening only.				
ECOG performance status	X	X				X		X	X		Within 24 hours prior to dosing.				
12-Lead electrocardiogram	X	X				X		X	X						
Hematology	X	X	X	X	X	X		X	X		Within 24 hours prior to dosing. More frequent assessments may be performed if clinically indicated				
Coagulation	X	X				X		X	X		Within 24 hours prior to dosing.				
Chemistry (serum or plasma)	X	X	X	X	X	X		X	X		Within 24 hours prior to dosing.				

Evaluation	Screening (Within 28 days of 1 st dose)	Treatment Period (1 cycle =28 days)						Notes	
		Cycle 1			Cycle ≥2				
		D1 (±3 days)	D8 (±3 days)	D15 (±3 days)	D22 (±3 days)	D1 (±3 days)	End of Cycle (±7 days)		
Pregnancy test	X Within 7 days						X		Serum pregnancy test required for WOCBP. Additional testing may be required by local regulations.
Ophthalmological examination	X			See Note					Examination to be performed by an ophthalmologist or qualified delegate at screening, 4-6 weeks after first dose, and as indicated if symptoms or signs of mineral deposits.
PK blood sampling				See Note					Pre-dose (from -30 min to just before dose), 1 h±30 min post-dose, and 3 h±30 min post-dose
ctDNA blood samples	X						X		
Tumor tissue sample	X								Archival or fresh tumor biopsy
Response assessments (CT/MRI)	X						X	X	At baseline and the end of every 2 cycles ±7 days), or as clinically indicated, until radiologic PD or initiation of new anticancer therapy (whichever comes first). For patients who discontinue treatment for reasons other than radiographic disease progression, imaging will be performed at EOT, (if the prior scan was performed ≥9 weeks) and during Survival Follow-up until radiologic disease progression or initiation of new anticancer therapy (whichever occurs first) unless patient withdraws consent.
Survival status								X	For all patients, unless patient withdraws consent or the study is terminated early by the Sponsor.

Table 2: Schedule of Events (Cohort C)

Evaluation	Screening (Within 28 days of 1 st dose)	Treatment Period (1 cycle =28 days)						End of Treatment (+7 days)	Safety Follow-up 30 days after last dose (+7 days)	Survival Follow-up Period (every 12±2 weeks)	Notes				
		Cycle 1				Cycle ≥2									

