11.5.3.1.2. Secondary Efficacy Analyses

Duration of response is a key efficacy endpoint:

- Duration of response will only be evaluated in patients with an objective response of CR or PR. Patients who are alive and progression-free as of the analysis cut-off date will be censored at their last evaluable response assessment prior to initiation of any new anticancer treatment. Patients who start subsequent anticancer therapy without a prior reported progression will be censored at the last response assessments prior to initiation of the subsequent anticancer therapy.

Additional efficacy endpoints include:

- Overall response rate and DCR based on Investigator assessment will be determined (per RECIST 1.1) as described for the primary analysis of ORR based on independent central review of radiologic images (Section [11.5.3.1.1](#)).
- Progression-free survival will be estimated using the Kaplan-Meier method. Patients who die without a reported disease progression will be considered to have progressed on the date of their death. Patients who did not progress or die will be censored on the date of their last response assessment. Patients who did not have any on-study assessments and did not die will be censored on the first dosing date. Patients who started any subsequent anticancer therapy without a prior reported progression will be censored at the last response assessment prior to initiation of the subsequent anticancer therapy.
- Overall survival will be analyzed in a similar manner to PFS. In the absence of confirmation of death or for patients who are alive as of the OS cut-off date, survival time will be censored at the last known date that the patient was alive.

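### The SAP's DCR rule ties the 6-week minimum to the first SD; read literally, it can fail a patient whose best overall response is SD

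*SAP*

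**What the plan says.** SAP Table 8 (Section 5.5.1) defines DCR as: "The proportion of patients experiencing a best overall response of SD, PR, or CR (per RECIST 1.1), based on IRC and Investigator assessment". DCR therefore follows from best overall response.

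SAP Section 5.5.1.1 takes the "best overall response recorded from the start of treatment until progression disease or start of subsequent new anticancer treatment". Its timing condition for SD is: "A minimum of a 6-week interval between initial of treatment (first dose date) and tumor measurement is required for SD". Footnote b to Table 9 repeats this: "A minimum of 6-week interval between initial of treatment (first dose date) and tumor measurement is required for SD". Neither sentence refers to the first SD.

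The DCR bullet in SAP Section 5.5.1.2 has its own timing condition: "A minimum of a 6-week interval is required between the first dosing date and the first SD".

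Protocol Section 11.5.3.1.2 has no such condition: "Overall response rate and DCR based on Investigator assessment will be determined (per RECIST 1.1) as described for the primary analysis of ORR". SAP Section 6 reports no change to the planned analyses.

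Protocol Table 1 (Schedule of Events, Cohorts A and B) sets response imaging as: "At baseline and the end of every 2 cycles ±7 days), or as clinically indicated". Scans outside the schedule are therefore allowed.

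**The concern.** The two sections put the same 6-week minimum on different objects. In Section 5.5.1.1 a later SD scan can satisfy it. In Section 5.5.1.2, as written, only the earliest SD scan can. Two patients with the same disease course could then be classified differently because one had an extra early scan, for example to investigate symptoms.

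The stakes are consistency and a possible downward error in a secondary endpoint. The best overall response table could list a patient under SD while the DCR table, from the same data, counts that patient as not having disease control. This could happen in the IRC read, the Investigator read or both, depending on which read calls the early scan SD.

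**Working it through.** The plan states no DCR figure, so there is nothing to reproduce. The check applies both rules to example scan histories and then sizes the effect per patient.

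**Inputs**
- Cycle length is 28 days (Protocol Section 5.1). Scans fall at the end of every 2 cycles, ±7 days, or when clinically indicated (Protocol Table 1).
- Minimum interval for SD: 6 weeks = 6 × 7 = 42 days (SAP Sections 5.5.1.1 and 5.5.1.2).
- Denominator: All Treated Population (SAP Section 5.5).
- Planned sizes: Cohort A 100, Cohort B 35 (Protocol Section 11.1). The SAP still gives 60 for Cohort A (Section 3.3).

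**Step 1: scheduled scans.** The first scheduled scan is at 2 × 28 = 56 days, with a window of 56 − 7 = 49 to 56 + 7 = 63 days. Since 49 > 42, a first SD on a scheduled scan meets both rules. They can differ only when a scan before day 42 is read as SD.

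**Step 2: are early scans excluded anywhere?** I found no rule that excludes them. The closest-to-target-date rule in SAP Section 5.1 covers laboratory records only. SAP Tables 10 and 12 count progression found between scheduled visits as an event, so off-schedule scans do enter efficacy derivations.

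**Step 3: apply both rules.** Rule 1 (Section 5.5.1.1): at least one SD measurement at day 42 or later, before PD. Rule 2 (Section 5.5.1.2, literal): the first SD is at day 42 or later.

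| Scan history (days from first dose) | Rule 1 | Rule 2, literal |
|---|---|---|
| SD 56, SD 112 | disease control | disease control |
| SD 49, SD 105 | disease control | disease control |
| SD 28, SD 56, SD 112, SD 168 | disease control | failure |
| SD 41, SD 56 | disease control | failure |
| SD 28, PD 56 | failure | failure |

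The third and fourth rows show the conflict. The last row shows that Rule 1 does not admit brief SD.

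**Step 4: size per patient.** An affected patient stays in the denominator and moves from success to failure, so DCR falls by 1/n:
- Cohort A: 1/100 = 1.0 point (1/60 = 1.7 points at the SAP's size).
- Cohort B: 1/35 = 2.9 points.

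**Step 5: illustration.** Assume a DCR of 60%, which is not in the documents, and 0 to 3 affected patients. Intervals are Clopper–Pearson 95%.

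| Affected patients | Cohort A | Cohort B |
|---|---|---|
| 0 | 60/100 = 60.0% (49.7–69.7) | 21/35 = 60.0% (42.1–76.1) |
| 1 | 59/100 = 59.0% (48.7–68.7) | 20/35 = 57.1% (39.4–73.7) |
| 3 | 57/100 = 57.0% (46.7–66.9) | 18/35 = 51.4% (34.0–68.6) |

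**The case against.** The strongest reply is that the two sections can be read together. If 6 weeks is a condition for SD to count at all, a day-30 scan yields no countable SD. The first SD is then the first qualifying one, for example day 56, and the patient passes. The definition of DCR by best overall response, and the protocol's link to the ORR derivation, point the same way. Nor does Section 5.5.1.2 say that later SD scans are ignored.

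This reading is reasonable and probably intended, but it is not written. The bullet says first SD, not first qualifying SD, and two programmers could code it differently. The reply does show that the failure is conditional on the literal reading.

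A reader might go further and infer that DCR will be biased downward by a few percentage points. The documents do not support that. They give no frequency for scans before day 42, and an affected patient needs all of these: an early off-schedule scan, a read of SD, SD at a later scan, and no confirmed CR or PR. Zero such patients is compatible with the plan.

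**Conclusion.** The wording conflict is real and minor. Read literally, the DCR sentence contradicts the SAP's own best-response rule and endpoint definition, and it adds a condition absent from the protocol. Under that reading the error can only lower DCR, by 1.0 point per affected patient in Cohort A and 2.9 points in Cohort B, in each read where the early scan is SD.

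This rests on two assumptions: that the sentence is programmed as written, and that at least one affected patient exists. Affected patients would be counted as failures, not removed from the analysis. Those with a later confirmed CR or PR still count as disease control. The primary ORR does not use the SD rule and is untouched. DCR is an additional secondary endpoint reported with a confidence interval, and the plan attaches no test or decision to it. The reason to act is that a stated rule can give a wrong result and is easily corrected.

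**What to change.** Replace the last sentence of the DCR bullet in SAP Section 5.5.1.2 with:

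*DCR uses the best overall response derived in Section 5.5.1.1; SD counts if at least one SD (or better) assessment, before PD or new anticancer therapy, is 6 weeks or more after the first dosing date.*

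Delete the reference to the first SD. The words *or better* are needed because Table 9 reclassifies an unconfirmed CR or PR as SD. The cut-off at PD or new therapy keeps the rule within the best-response window of Section 5.5.1.1.

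The cost is one SAP sentence. No new data are needed, and results do not change for patients scanned on schedule.
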